7.1.2 G305

G305 is comprised of recombinant NY-ESO-1 full-length protein with a His-tag that is cleaved prior to final purification (182 amino acids and ~ 18 kDa), which is mixed with GLA-SE to form a 2% oil/water emulsion. GLA is a synthetic Lipid A analog that can bind to the TLR4 receptor activating the innate immune response in a number of different immune cells including DCs.⁶ G305 can induce the activation of a potent adaptive immune response against NY-ESO-1 involving antibodies, CD4⁺ T cells, and other effector immune cells. For further information regarding G305, its components, properties, and formulation, please consult the CMB305 IB.⁶

7.1.2.1 Investigational Drug Packaging and Labeling

The Investigational Drug Product G305 will be supplied in a 2-vial configuration. One vial will contain the formulated protein antigen NY-ESO-1 and the second vial will contain the adjuvant GLA-SE.

Along with GLA, the GLA-SE formulation contains squalene (oil), glycerol, tocopherol (vitamin E), 1,2-dimyristoyl-sn-glycero-3-phosphocholine (DMPC), surfactant (polaxamer), and ammonium phosphate buffer.

NY-ESO-1 protein will be packaged as 500 µg of protein/mL in 2 mL vials, each containing 0.65 mL of formulated protein. GLA-SE will be packaged in 3 mL clear glass vials each containing 0.8 mL of formulated adjuvant.

Detailed instructions for admixing the protein with adjuvant will be provided in the Pharmacy Manual.

7.1.2.2 Storage and Disposition of the Investigational Drug Products

The NY-ESO-1 protein must be stored at **-60°C (or colder)**. GLA-SE is an emulsion that must be stored at **2 to 8°C**. **GLA-SE MUST NOT BE FROZEN**. Upon completion of the study, all remaining materials must be returned to IMDZ unless otherwise instructed.

7.1.2.3 Dose Preparation for Administration to the Patient

Dose preparation instructions will be provided in the Pharmacy Manual. One (1) mL of the mixed product will be administered via IM injection in the deltoid or femoral region (anterior upper thigh) using alternating limb inject sites on Days 28, 56, and 84 as outlined in the Schedule of Events ([Table 1](#) and [Table 2](#)) and the Pharmacy Manual.

7.1.3 Atezolizumab

Atezolizumab (formerly MPDL3280A) is an anti-PD-L1 human IgG1 mAb consisting of 2 heavy chains (448 amino acids) and 2 light chains (214 amino acids) produced in Chinese hamster ovary (CHO) cell. It was engineered with a single amino acid substitution (asparagine to alanine) at position 298 of the heavy chain resulting in non-glycosylated antibody minimizing its ability to bind to Fc-receptors. This loss of binding eliminates Fc-effector function and depletion of PD-L1 expressing cells. Atezolizumab is being investigated as a potential therapy in humans against solid tumors and hematologic malignancies. Atezolizumab is contraindicated for patients with a history of severe allergic anaphylactic reactions to chimeric, human or humanized antibodies, or fusion proteins, as well as for patients with known hypersensitivity to CHO cell products or any component of the atezolizumab formulation.

7.1.3.1 Investigational Drug Packaging and Labeling

The atezolizumab drug product is provided in a single-use, 20-mL glass vial as a colorless-to-slightly-yellow, sterile, preservative-free clear liquid solution intended for IV administration. The vial is designed to deliver 20 mL (1200 mg) of atezolizumab solution but may contain more than the stated volume to enable delivery of the entire 20 mL volume. The atezolizumab drug product is formulated as 60 mg/mL atezolizumab in 20 mM histidine acetate, 120 mM sucrose, 0.04% polysorbate 20, pH 5.8.

For further details, see the atezolizumab Pharmacy Manual and IB.

7.1.3.2 Storage and Disposition of the Drug Product

Atezolizumab must be refrigerated at 2°C to 8°C (36°F to 46°F) upon receipt until use. Atezolizumab vials should not be used beyond the expiration date provided by the manufacturer. No preservative is used in atezolizumab drug product; therefore, the vial is intended for single use only. Discard any unused portion of drug left in a vial. Vial contents should not be frozen or shaken and should be protected from direct sunlight. Upon completion of the study, all remaining materials must be returned to IMDZ.

7.1.3.3 Dose Preparation for Administration to the Patient

Administration of atezolizumab will be performed in a setting with emergency medical facilities and staff who are trained to monitor for and respond to medical emergencies. A dose of 1200 mg atezolizumab will be administered by IV infusion every 3 weeks. The investigational products will be delivered in infusion bags with IV infusion lines with product contacting surfaces of polyvinylchloride (PVC) and polyolefin and 0.2 µm in-line filters (filter membrane of polyethersulfone). No incompatibilities have been observed between atezolizumab and PVC or polyolefin infusion materials (bags and infusion lines).

Specific instructions for the preparation and administration of the atezolizumab infusion solution are contained within the Pharmacy Manual.

7.2 Treatment Administration

For patients randomized to the combination treatment arm, the dosing regimens for LV305 and G305 will mimic those used in previous Phase 1 studies. The dose of each agent will be given according to the schedules outlined in [Table 1](#) (combination dosing arm with atezolizumab) or [Table 2](#) (control arm).

Two doses of LV305 will be administered 2 weeks apart on Weeks 0 and 2, which will be followed every 2 weeks with G305 alternating with LV305 ([Figure 1A](#)). The alternating regimen that will be used was designed primarily to maximize the induction of CD8 T-effector/memory cells by LV305 and then expand or boost them with the G305. Nonclinical studies suggest that injections every 2–4 weeks generate the most durable and highest magnitude immune responses^{6,20} and that the responses continue to be boosted with additional treatments.

Patients will be given an IV infusion of 1200 mg atezolizumab over 30 to 60 minutes every 3 weeks starting on Day 0 until disease progression or unacceptable toxicity ([Figure 1A&B](#)). The initial dose of atezolizumab will be delivered over 60 (± 15) minutes. If the first infusion is

tolerated without infusion-associated AEs, the second infusion may be delivered over 30 (\pm 10) minutes. If the 30-minute infusion is well tolerated, all subsequent infusions may be delivered over 30 (\pm 10) minutes. For the first infusion, the patient's vital signs (HR, respiratory rate, BP, and temperature) should be measured within 15 minutes of the infusion, during the 60-minute infusions (every 15 [\pm 5] minutes), and 30 minutes after the infusion. For subsequent infusions, vital signs do not need to be obtained during the infusion if the prior infusion was tolerated without symptoms. The management of any infusion-related reactions are outlined in [Section 7.4.4.1](#).

Patients in both study arms will be treated with atezolizumab therapy alone every 3 weeks starting at from Day 0 until disease progression or unacceptable toxicity. Due to administrative reasons, atezolizumab treatment may be administered up to 3 days before or after the scheduled dosing day.

Any overdose or incorrect administration of study drug should be noted on the Study Drug Administration electronic Case Report Form (eCRF). AEs associated with an overdose or incorrect administration of study drug should be recorded on the Adverse Event eCRF. Further details are provided in [Section 9.4.1](#).

7.2.1 Randomization

Patients will be randomized 1:1 to the combination dosing arm or control arm of the study no more than 4 days prior to dosing (Day 0). Randomization will be stratified by type of disease.³⁰ An automated interactive web response system (IWRS) will be used to manage the randomization and treatment assignment. Patients who withdraw from the study will not be replaced. Refer to the Study Reference Manual for details on randomization and registration.

7.2.2 Dose Modification Guidelines

Dosing interruptions are permitted in case of medical/surgical events or logistical reasons not related to study therapy (e.g., elective surgery, unrelated medical events, patient vacation, and/or holidays). Patients should be placed back on study therapy within 3 weeks of scheduled interruption, unless otherwise discussed with Sponsor. The reason for interruption should be documented in the patient's study records.

There are no adjustments for dose delay for a given patient, and treatment delays for the CMB305 components that are >14 days from the treatment plan before Visit 12 will not be allowed. During the study, if a patient experiences a DLT, treatment of that patient will be suspended. A patient may be considered for receiving further injections of the LV305, G305, or atezolizumab investigational drug product on a case-by-case basis following evaluation of the benefit/risk ratio to the patient by the Investigator and Medical Monitor, in consultation with the

independent DMC (e.g., for patients who have experienced a tumor response and had a non-life- and non-organ-threatening DLT, continuation of treatment as per protocol may be considered).

No reduction or modification of the atezolizumab dose will be allowed. Any toxicities associated or possibly associated with atezolizumab treatment should be managed according to standard medical practice. Additional tests, such as autoimmune serology or biopsies, may be used to determine a possible immunogenic etiology. As a result, study treatment must be withheld for AEs or infusions reactions associated with atezolizumab treatment as outlined in [Appendix F](#).

While most irAEs observed with immunomodulatory agents have been mild and self-limiting, such events should be recognized early and treated promptly to avoid potential major complications. The primary approach to Grade 1-2 irAEs is supportive and symptomatic care; for higher grade irAEs, steroids by mouth or parenterally are given, and either skipping a dose or stopping therapy is appropriate. Recurrent Grade 2 irAEs may also mandate skipping a dose of atezolizumab or the use of steroids as outlined in [Appendix F](#).

Discontinuation of atezolizumab may not have immediate therapeutic effect, and there is no available antidote for atezolizumab. In severe cases, immune-related toxicities may be acutely managed with topical corticosteroids, systemic corticosteroids, or TNF α inhibitors as outlined in [Appendix F](#).

7.3 Drug Accountability

Under no circumstances is it permitted to use study supplies for any purposes other than those specified in this Protocol.

The Investigator or medically qualified, authorized delegate will be provided with forms to enable accurate recording of all study doses at the study facility at all times. The Investigator, or designee, must sign a statement that he/she has received study injections intended for the study. At any given time, the figures of supplied, used, and remaining doses of study drug must match. At the end of the study, it must be possible to reconcile delivery records with those of used and unused stocks. Account must be given of any discrepancies.

7.4 Prior and Concomitant Therapy

7.4.1 Prior Therapy

Any investigational agent or cancer therapy is prohibited during the 21 days prior to Day 0, including chemotherapy, radiation, kinase inhibitors, immunotherapy, G-CSF, GM-CSF, or other biologics. Systemic corticosteroid use is not permitted within four weeks prior to dosing. Patients who have previously received NY-ESO-1 directed immunotherapies or any antibody or drug targeting T-cell costimulation will not be eligible.

7.4.2 Prohibited Concomitant Therapy

Any concomitant therapy intended for the treatment of cancer, whether health authority–approved or experimental, is prohibited. The following treatments are prohibited during study until the end of the study or tumor progression:

- Any chemotherapy, hormonal therapy, immunotherapy, radiotherapy, herbal therapy, or investigational drug other than LV305, G305, or atezolizumab.
- Any corticosteroid (>10 mg/day prednisone or equivalent dose) within 3 weeks of first study treatment and during the study period. However, systemic glucocorticoids are permitted to modulate symptoms for an MEOI of suspected immunologic etiology.
- Other concurrent immunosuppressive medications such as methotrexate, cyclosporine, and azathioprine.
- Live vaccines within 30 days prior to the first dose of trial treatment and while participating in the trial. Examples of live vaccines include, but are not limited to, the following: measles, mumps, rubella, chicken pox, yellow fever, rabies, BCG, and typhoid (oral) vaccine. Seasonal influenza vaccines for injection are generally killed virus vaccines and are allowed. However, intranasal influenza vaccines (e.g., FluMist®) are live attenuated vaccines, are not allowed.

No premedication will be allowed for the first dose of atezolizumab. Premedication may be administered for subsequent infusions at the discretion of the treating physician after consultation with the Medical Monitor.

After Day 84, certain forms of radiotherapy may be considered for pain palliation if patients are deriving benefit (e.g., treatment of known bony metastases).

Patients experiencing a mixed response requiring local therapy (e.g., surgery, stereotactic radiosurgery, radiotherapy, and radiofrequency ablation) for control of three or fewer lesions may still be eligible to continue study treatment. Patients who receive local therapy directed at a target lesion will no longer be evaluable for radiographic response but will remain evaluable for progression. Such cases must be discussed with and approved by the Medical Monitor.

There are no known procedure-related risks with use of atezolizumab. The following therapies are excluded while patients are receiving study drug:

- Patients who are receiving a receptor activator of nuclear factor kappa B ligand (RANKL) inhibitor (denosumab) prior to enrollment must be willing and eligible to receive a bisphosphonate instead; denosumab could potentially alter the activity and the safety of atezolizumab.

- Immunostimulatory agents not part of study treatment, including but not limited to IFN- γ or IL-2; these agents, in combination with atezolizumab, could potentially increase the risk for autoimmune conditions.
- Immunosuppressive medications, including but not limited to cyclophosphamide, azathioprine, methotrexate, and thalidomide; these agents could potentially alter the activity and the safety of atezolizumab. Systemic corticosteroids, TNF- α inhibitors, mycophenolate and other immune suppressants may be administered for the treatment of immune-related toxicities at the discretion of the treating physician after consultation with the Medical Monitor.

In addition, all patients should not receive other immunostimulatory agents for 10 weeks after the last dose of atezolizumab. Atezolizumab is not metabolized via cytochrome P450 enzymes or conjugation/glucuronidation reactions. No drug interaction studies for atezolizumab have been conducted or are planned. There are no known interactions with other medicinal products or other form of interactions.

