10.2.2.4 Efficacy Analyses

10.2.2.4.1 Primary Efficacy Analysis

The primary efficacy analysis will be the evaluation of OS and PFS based on the ITT Population.

Overall survival is defined as the time interval from randomization to death of any cause. Patients who are alive will be censored at the last known date alive or data analysis cutoff date, whichever is earlier. PFS is defined as the time interval from randomization to tumor progression or death. Accordingly, the precise definition of progression and the timing of imaging scans to progression are very important. Every effort must be made to assure that timeframes for follow-up imaging scans are achieved, so that both treatment groups can be usefully compared. Assessments must be adequate to evaluate target lesions, non-target lesions, and to search for new lesions.

PFS will be based on RECIST 1.1 response guidelines modified to use irRC-specific confirmation. PFS will be defined as the time from randomization to disease progression or death (any cause), whichever occurs first. The irRC modification requires a confirmation of progressive disease (PD) at least 4 weeks later with imaging; once confirmed, the date of progression is defined as the first date that the total tumor burden was shown to have increased by at least 20% compared with the nadir. Patients who do not have disease progression or have not died will be censored at the date when the last tumor assessment determines a lack of progression. If a patient begins a new anti-cancer therapy or has radiotherapy or surgery at a lesion site prior to confirmed progression (or death), the patient will be censored at the last assessment where the patient was documented as progression free prior to the intervention. Patients with two or more missing response assessments prior to a visit with progression (or death) will be censored at the last visit where the patient is documented to be progression free.

The primary efficacy analysis will be the evaluation of OS and PFS using Kaplan-Meier methodology and will be performed on the ITT Population for each treatment arm. Kaplan-Meier plots and 95% confidence intervals (CIs) for 75%, 50% and 25% survival, if reached, will be provided for each treatment group.

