# **5 STUDY ENDPOINTS**

# 5.1 Efficacy Endpoints

# 5.1.1 Primary Efficacy Endpoint

# 5.1.1.1 **Progression free Survival (PFS)**

PFS will be based on RECIST 1.1 response guidelines modified to use irRC-specific confirmation. Progression-free survival (PFS) in months is calculated as: (date of first progression or death (any reason) – date of randomization +1)/30.4375. The irRC modification requires a confirmation of progressive disease (PD) at least 4 weeks later with imaging; once confirmed, the date of progression is defined as the first date the total tumor burden was shown to have increased by at least 20% compared with nadir. Patients without progression or death are censored at the date of the last disease assessment. If a patient begins a new anti-cancer therapy or has radiotherapy or surgery at a lesion site prior to confirmed progression (or death), the patient will be censored at the last assessment where the patient was documented as progression free prior to the intervention. Patients with two or more missing response assessments prior to a visit with progression (or death) will be censored at the last visit where the patient is documented to be progression free. Patients without disease assessment post-baseline will be censored at the randomization date. As needed, we will use Table 3 to specify how dates of progression events and dates for censoring of progression data are assigned. Table 3 represents an analysis that only includes well-documented and verifiable progression events. In Table 3, the progression dates are:

- Based only on radiological assessments verified by an IRC and symptomatic deterioration date assessed by study investigator.
- Assigned to the first time when tumor progression was noted.
- The date of death when the patient is closely followed. However, deaths occurring after two or more missed tumor assessments (> 91 days after last tumor assessment) are censored at the last visit.

Progressive disease will be assessed by the unidimensional measurements approach of the Immune-related Response Criteria.

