Death before first PD assessmentDate of deathProgressedDeath between adequate assessment visitsDate of deathProgressedDeath or progression after two or more missed visitDate of last tumor assessmentCensoredNew anti-cancer therapy or radiotherapy or surgery at a lesion siteDate of last tumor assessment where the patient was documented as progression free prior to the interventionCensored	more missed visit		
Death between adequate assessment visitsDate of deathProgressedDeath or progression after two or more missed visitDate of last tumor assessmentCensoredNew anti-cancer therapy or radiotherapy or surgery at a lesion siteDate of last tumor assessment where the patient was documented as progression free prior to the interventionCensored	Death before first PD assessment	Date of death	Progressed
visits       Death or progression after two or more missed visit       Date of last tumor assessment       Censored         New anti-cancer therapy or radiotherapy or surgery at a lesion site       Date of last tumor assessment where the patient was documented as progression free prior to the intervention       Censored	Death between adequate assessment	Date of death	Progressed
Death or progression after two or more missed visitDate of last tumor assessmentCensoredNew anti-cancer therapy or radiotherapy or surgery at a lesion siteDate of last tumor assessment where the patient was documented as progression free prior to the interventionCensored	visits		
missed visit     Date of last tumor assessment where the patient was     Censored       New anti-cancer therapy or radiotherapy or surgery at a lesion site     Date of last tumor assessment where the patient was     Censored	Death or progression after two or more	Date of last tumor assessment	Censored
New anti-cancer therapy or radiotherapy or surgery at a lesion siteDate of last tumor assessment where the patient was documented as progression free prior to the interventionCensored	missed visit		
radiotherapy or surgery at a lesion site   documented as progression free prior to the intervention	New anti-cancer therapy or	Date of last tumor assessment where the patient was	Censored
	radiotherapy or surgery at a lesion site	documented as progression free prior to the intervention	
prior to confirmed progression (or	prior to confirmed progression (or		
death)	death)		
No progression or Death         Date of last tumor assessment         Censored	No progression or Death	Date of last tumor assessment	Censored

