# 5.1.3 Exploratory Efficacy Endpoints

# 5.1.3.1 Tumor Growth Rate and Progression Arrest Rate

Progression status as determined by investigator performed by using outside images off protocol at screening will be collected in study.

At the baseline tumor assessment, the sum of the longest diameters (SLD) of all index lesions (2 target lesions per organ, up to 5 target lesions in total) will be calculated. At each subsequent tumor assessment, the SLD of the index lesions and of new, measurable lesions is calculated: SLD = SLD index lesions + SLD new, measurable lesions

Percentage changes in SLD per assessment time point describe the size and growth kinetics of both conventional and new, measurable lesions as they appear.

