# 5.1.3.2 Overall Response Rate (ORR) and Duration of Response (DOR)

Overall response rate (ORR) will be defined as the number of patients whose best overall response is complete response (irCR) or partial response (irPR) divided by the number of evaluable patients. Overall response rate based on unconfirmed response and confirmed response will both be summarized.

Duration of response (DOR) will be defined only for the patients whose confirmed best response is irCR or irPR as the time interval between the date of the earliest qualifying confirmed response and the date of progressive disease (PD) or death for any cause, whichever occurs first. DOR in months will be calculated as: (date of PD or death, whichever occurs first – date of first confirmed irCR or irPR + 1)/30.4375.

For patients who are alive without documentation of disease progression following the qualifying response, duration of response will be censored following the same rule defined for PFS.

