# 8 CHANGES FROM THE PROTOCOL SPECIFIED STATISTICAL ANALYSES

If discrepancies exist between the text of the statistical analysis as planned in the protocol, and the final SAP, a protocol amendment will not be issued, and the SAP will prevail.

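### Protocol 7.4.2 keeps locally treated patients evaluable for progression but not for response; the PFS definition in both documents censors them, and the SAP has no rule for their response

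*Protocol*

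**What the plan says.** **What is allowed.** Under Protocol 7.4.2, patients with a mixed response who need surgery, radiotherapy, radiosurgery or radiofrequency ablation "for control of three or fewer lesions may still be eligible to continue study treatment", with Medical Monitor approval. The section then gives two evaluation rules: "Patients who receive local therapy directed at a target lesion will no longer be evaluable for radiographic response but will remain evaluable for progression".

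**PFS.** Protocol 10.2.2.4.1 covers new anti-cancer therapy, and radiotherapy or surgery to a lesion, before confirmed progression or death: "the patient will be censored at the last assessment where the patient was documented as progression free prior to the intervention". SAP 5.1.1.1 has the same rule: a patient who "has radiotherapy or surgery at a lesion site prior to confirmed progression (or death), the patient will be censored at the last assessment" that showed no progression. SAP Table 3 has a row for "New anti-cancer therapy or radiotherapy or surgery at a lesion site" with the outcome Censored. The 6-month PFR is a Kaplan-Meier estimate (SAP 5.1.2.1). SAP 7.6.2.1 reads a signal from it when the lower 80% confidence limit exceeds 25%.

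**Response.** SAP 5.1.3.1: "At each subsequent tumor assessment, the SLD of the index lesions and of new, measurable lesions is calculated". Protocol Appendix D defines irPR by a fall in tumor burden of at least 30% from baseline, confirmed at least 4 weeks later, whatever the cause of the fall. SAP 5.1.3.2 defines ORR as the "number of patients whose best overall response is complete response (irCR) or partial response (irPR) divided by the number of evaluable patients"; CBR in 5.1.3.3 has the same form. SAP 7.6.3.2 runs ORR on the ITT and EE sets, and the Efficacy set in SAP 6.3 does not exclude patients who had local therapy.

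**Precedence.** Where the two documents differ on the statistical analysis, SAP 8 says "a protocol amendment will not be issued, and the SAP will prevail".

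**The concern.** For progression, the plan gives two incompatible instructions. One keeps the patient at risk after local therapy; the other stops the clock at the last scan before it. A mixed response that needs local control suggests that some disease is not controlled, so these patients may well be closer to progression than those who remain. Censoring them may therefore be informative. It affects primary PFS and, through Kaplan-Meier, the secondary 6-month PFR.

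For response, 7.4.2 states a sound principle that nothing in the SAP carries out. As the SAP reads, a resected target lesion can pass for drug effect in best response, ORR, CBR and the SLD plots, and in the SAP 7.7 subgroups defined by on-study response.

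The trial is open-label and the investigator initiates the procedure. If use differs between arms, PFS, ORR and CBR would move for reasons unrelated to CMB305.

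**Working it through.** **1. The plan's own figures.** Neither document gives a figure for local therapy. The nearest one that rests on the PFS rule is the 6-month PFR design in Protocol 10.3 and 10.3.1.
- PFR = exp(−ln 2 × 6 / median). A median of 3 months gives 25.0%, and 5.2 months gives 44.9%, matching 25% and 45%.
- Exact two-stage calculation (at least 6 of 18, then at least 14 of 40): type I error 0.080 and power 0.856, against the stated 0.1 and 0.85.

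The design reproduces, and this point does not dispute it.

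**2. The two PFS rules side by side**

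| | Protocol 7.4.2 | Protocol 10.2.2.4.1; SAP 5.1.1.1 and Table 3 |
|---|---|---|
| Lesion treated | target lesion | any lesion site |
| Procedures named | surgery, radiosurgery, radiotherapy, ablation | radiotherapy, surgery, new anti-cancer therapy |
| Later progression | patient still evaluable | not counted; censored before the procedure |

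**3. Possible effect on 6-month PFR (illustration; all inputs assumed).** Take an arm of 40 with 30 progressions by 6 months: 11, 8, 6 and 5 at four 6-weekly scans. With everyone kept at risk, PFR = 10/40 = 25.0%. Now suppose k patients are censored one scan before they would have progressed.
- Censored at scan 1: S = (29/40) × 10/(29 − k).
- Censored at scan 2: S = (21/40) × 10/(21 − k).

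| k | scan 1 | scan 2 |
|---|---|---|
| 1 | 25.9% | 26.3% |
| 3 | 27.9% | 29.2% |
| 5 | 30.2% | 32.8% |

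The highest lower 80% limit among these is 22.8% (k = 5, scan 2, log-log), still below 25%.

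**4. Response.** Take three 40 mm target lesions, a sum of 120 mm (the 12 cm limit for synovial sarcoma). Assume that a resected lesion is scored 0 mm.
- Resect one: (120 − 80)/120 = 33.3% fall, which meets irPR.
- The irPR threshold is 120 × 0.70 = 84 mm. The other two lesions could grow from 80 to 84 mm and the next scan would still confirm irPR.
- With a 60 mm baseline, excising 20 mm gives −33.3%. If the rest grows by 2 mm, (42 − 60)/60 = −30.0%, still irPR.
- One such patient is 1/40 = 2.5 ORR points. If 1 to 4 patients per arm were affected (assumed), the range is 2.5 to 10 points, provided that every one of them becomes a false responder.

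**5. DOR.** Protocol 10.2.2.6.2 applies the PFS event and censoring rules to DOR. SAP 5.1.3.2 does so for patients alive without documented progression. Suppose the last scan before surgery is on Day 84 and the response is first seen on Day 126. Then DOR = (84 − 126 + 1)/30.4375 = −1.3 months: the response is censored before it starts.

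**The case against.** The strongest reply is that the SAP does not depart from the Protocol on PFS. Protocol 10.2.2.4.1 has the same censoring, so the SAP follows the Protocol's own endpoint definition. That is correct. The conflict lies inside the Protocol, and editing only the SAP would create a new one.

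On response, the SAP is silent rather than contrary. The denominator of evaluable patients, and the not-evaluable category that SAP 7.6.3.2 tabulates, leave room for 7.4.2 to operate. This stands in part. But neither document defines evaluable for ORR, and the ITT and EE analyses state no exclusion, so a programmer following the SAP would count the response.

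Remaining evaluable for progression might mean only continued scanning for treatment decisions. That is possible, but the text does not say so, and an analyst cannot tell.

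Finally, the sizes are constructed. No frequency of local therapy is given, and the Study Reference Manual, which holds the full RECIST definitions, may say how a resected lesion is scored. In the illustration the 80% limit never crosses 25%. ORR, CBR, tumor growth and the between-arm comparisons are exploratory, and primary PFS is a per-arm Kaplan-Meier description. All of this stands and limits the weight of the point.

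**Conclusion.** The point holds in two parts. For progression there is an explicit contradiction between Protocol 7.4.2 and the PFS definition in both documents. For response there is an omission: no SAP rule stops procedure-made shrinkage from counting as irPR, and DOR then breaks down for that patient. Each such patient is worth 2.5 ORR points in an arm of 40. The PFR shift in the illustration is about 1 to 8 percentage points for one to five patients. Both depend on an unstated frequency of use and on the scoring assumption above. It should be corrected, but it does not undermine the design.

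A reader might infer more than the documents support:
- That the SAP reverses 7.4.2 on response. It says nothing either way.
- That these patients are removed from PFS. They contribute follow-up until censoring, and OS is unaffected.
- That the lowered nadir distorts PFS. In the example, irPD would be called at 80 × 1.20 = 96 mm, which is 20% below baseline. Once a patient has been censored, that cannot move PFS. It matters only if the patient stays at risk.
- That ablation escapes censoring. It may fall under new anti-cancer therapy; the wording leaves this open.
- That 7.4.2 requires the treated lesion to be dropped from the sums. It does not say so.

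**What to change.** 1. **Response (SAP 5.1.3.1 to 5.1.3.3 and 7.6.3).** After local therapy to a target lesion, take best overall response and SLD change only from scans before the procedure. Keep the patient in the ITT denominator, and define evaluable for ORR and CBR.
2. **PFS (Protocol 7.4.2 and 10.2.2.4.1; SAP 5.1.1.1 and Table 3).** Reconcile these so that one primary rule applies in both documents. Prespecify the other as a sensitivity analysis for PFS and 6-month PFR: censoring at local therapy versus staying at risk for later progression or death. The at-risk version needs a sentence on how the treated lesion enters the sum and the nadir, since no current text covers it.
3. **Procedures.** Use one list (surgery, radiosurgery, radiotherapy, ablation) in all these sections. Confirm that ablation is captured: Protocol 5.1 and 6.3 name only radiotherapy and surgeries for recording.

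The cost is wording in both documents, one extra analysis run and a check of the case report form. ORR may fall slightly. These are analysis rules only; who may receive local therapy does not change.
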